#### 9.7 Appropriateness of procedures / measurements

All efficacy and safety parameters, as well as the methods to measure them, are standard variables / methods in clinical studies and / or clinical and gynecological practice. They are widely used and generally recognized as reliable, accurate and relevant.

#### 10 Statistical measures and determination of sample size

#### 10.1 General considerations

Statistical analysis will be performed using SAS (statistical analysis system); the version used will be specified in the statistical analysis plan. All data will be listed and study summary tables will be provided where appropriate. Quantitative data will be described by the following summary statistics: arithmetic mean, standard deviation, median, minimum and maximum. Where appropriate, summary statistics will be provided for the original data as well as for the change versus baseline. Graphical illustrations will be provided where appropriate. Frequency tables will be provided for qualitative data. Due to the exploratory character of this study, no confirmatory analysis will be done. All calculated p-values and confidence intervals are to be interpreted in the exploratory sense.

Data from patients who are transferred to a roll-over study may be pooled and analyzed together with the data from the study in which the patient was initially included. The results from these analyses will be reported separately.

#### 10.2 Analysis sets

All subjects who received at least one dose of the study medication will be included in the safety evaluation. All subjects who completed Cycle 1 or discontinued during Cycle 1 due to an adverse event or DLT will be included in the MTD evaluation. All subjects who have received at least one dose of BAY 1163877 and who have post-baseline efficacy data available will be included in the efficacy evaluations.

All subjects with valid pharmacokinetic data will be included in the evaluation of pharmacokinetic concentrations and parameters.

Subjects to be included in the relative bioavailability evaluation ("tablet bridging cohort") should have evaluable pharmacokinetic data on both Cycle 1, Day -3 and Cycle 1, Day 1.

No. BAY 1163877 / 16443

17 Oct 2018 Version 8.0 Page: 105 of 395

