## 7.2 Withdrawal of subjects from study

#### 7.2.1 Withdrawal - amended

Subjects will be withdrawn from the study for the following reasons:

- Consent withdrawal
  - At their own request or at the request of their legally acceptable representative
  - At any time during the study and without giving reasons, a subject may decline to participate further. The subject will not suffer any disadvantage as a result.
- Substantial non-compliance with study procedures
  - Subject who is off study drug (BAY 1163877) longer than 8 consecutive days in Cycle 1
  - Subjects lost to follow-up
- Violation of in- / exclusion criteria (subject no longer eligible for the study)
  - If the subject develops conditions which would have prevented his / her entry into the study according to the in- / exclusion criteria, he / she must be withdrawn immediately if safety is concerned; in other cases, the investigator will decide whether there is a conflict with the study objectives.
  - The development of a second malignancy that requires a different treatment.
  - Development of any intercurrent illness or situation which may, in the judgment of the investigator, affect assessments of clinical status and study endpoints to a relevant degree.
  - Subjects with a positive urine beta-HCG test confirming pregnancy. Pregnancy will be reported under the same timelines as a serious adverse event.
- Unacceptable toxicity
  - If, in the investigator's opinion, continuation of study would be harmful to the subject's well-being
  - Severe allergic reactions, such as exfoliate erythrodermia, anaphylaxis, or vascular collapse
  - Any other potential adverse reaction deemed sufficiently serious to warrant discontinuation of treatment by the investigator or his designated associate(s).
  - Use of illicit drugs or other substances that may, in the opinion of the investigator or his designated associate(s), have a reasonable chance of contributing to toxicity

No. BAY 1163877 / 16443

17 Oct 2018 Version 8.0 Page: 54 of 395

or otherwise confound the results.

- Retinal detachment of grade 2 or higher according to CTCAE v4.03 46
- AST/ALT > 3xULN with concomitant bilirubin > 2xULN in the absence of another reason for these elevations
- AST/ALT > 8xULN or AST/ALT > 5xULN for > 2 weeks if no other reason is found for these elevations
- Tumor progression

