## 7.2.2 Replacement

Subjects who discontinue due to a DLT will NOT be replaced.

Subjects who discontinue during the first cycle of therapy (Cycle 1) due to any reason other than a DLT and / or related toxicity, and subjects who took less than 80% of the required study drug (BAY 1163877) in Cycle 1 (see Section 8.7) will be replaced to ensure 3 evaluable subjects per cohort for the determination of MTD and PK of BAY 1163877. Subjects who discontinue after the first cycle (Cycle 1) will not be

 Withdrawal criteria were added by Amendment 6, see section 15.6.2.12

17 Oct 2018 Version 8.0 Page: 55 of 395

replaced.

Subjects enrolled in Study Part 1 / MTD expansion (all comer) with insufficient paired biopsy samples will be replaced to ensure at least 10 subjects with paired biopsy samples for p-ERK1/2 analysis.

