## 8.7 Treatment compliance

#### **Treatment compliance**

The first administration of study medication (BAY 1163877) will be done with a member of the site team. This person will ascertain and document that the subject receives the treatment as planned.

On the following days the subject will self-administer (or a caregiver will administer) BAY 1163877 after he / she has been informed about the correct dosing schedule.

Plasma / serum concentrations will give additional information about the subjects' treatment compliance.

At home, subjects will document the intake of study drug (date and time of dosing) as well as the administered dose on a compliance sheet / paper diary (source document to verify treatment compliance), see Section 9.6.1.

The packages of study medication have to be brought back to the trial site for an additional control.

Compliance will be evaluated by the investigational site based on drug accountability.

The information recorded in the paper diary will be transferred into the eCRF taking into account each dose interruption and / or any individual changes in dosing.

A compliance of at least 80% is required, meaning documented intake of at least 80% of the planned study medication (80 % = 32 doses or 16 days in Cycle 1 with PK assessment [Part 1 and Part 2 only] and 34 doses or 17 days in  $\geq$  Cycles 2 and in Cycle 1 without PK assessment [including Part 3]). 

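### Sections 7.2.2 and 10.2 define MTD evaluability differently, so subjects replaced as non-evaluable can still be counted as DLT-free in the MTD analysis

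*Protocol*

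**What the plan says.** Section 10.2 fixes the set for the primary variable: "All subjects who completed Cycle 1 or discontinued during Cycle 1 due to an adverse event or DLT will be included" in the MTD evaluation. It sets no intake condition, and the adverse event need not be related to study drug.

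Section 7.2.2 decides who is replaced.
- Under-dosing: "subjects who took less than 80% of the required study drug (BAY 1163877) in Cycle 1 (see Section 8.7) will be replaced".
- Stopping in Cycle 1: replaced if this is "due to any reason other than a DLT and / or related toxicity".
- Purpose: to secure three "evaluable subjects per cohort for the determination of MTD and PK of BAY 1163877".
- Exemption: "Subjects who discontinue due to a DLT will NOT be replaced". Nothing is said about a subject who has a DLT and does not discontinue.

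Section 8.7 turns 80% into "32 doses or 16 days in Cycle 1 with PK assessment" (Parts 1 and 2), and 34 doses or 17 days in a Cycle 1 without PK assessment.

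Section 7.2.1 lists under non-compliance, as a reason for withdrawal, "Subject who is off study drug (BAY 1163877) longer than 8 consecutive days in Cycle 1". Section 8.4.3 allows the next dose after a Cycle 1 DLT to be delayed by up to 21 days, under a stated condition.

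**The concern.** Section 7.2.2 replaces certain subjects because they are not informative about the dose. Section 10.2 then admits some of the same subjects to the MTD evaluation, where they count as having tolerated it. Cycle 1 DLT incidence is the primary variable (Section 6.1). It drives the logistic model (Section 10.4.2) and the count-based limits on further dosing (Section 6), with cohorts of 3 to 9, so one or two subjects in the denominator matter. A DLT-free subject who took much less than the planned dose says little about whether that dose is tolerable.

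The replacement rule also has a gap. Subjects with a DLT are among those most likely to have drug withheld and so to fall below 80%, yet the exemption names only those who discontinue.

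**Working it through.** **1. Reproduce the protocol's threshold.** With PK assessment (all of Part 1), Cycle 1 has one dose on Day 1, none on Day 2, and two daily for 19 days (Section 6, Treatment).
- Planned: 1 + 19 × 2 = 39. Required: 0.80 × 39 = 31.2, rounded up to 32 doses. This matches Section 8.7.
- Without PK: 21 × 2 = 42; 0.80 × 42 = 33.6, rounded up to 34. This also matches.

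**2. Does the contested group exist?** Assume the days off fall in the twice-daily period and no other dose is missed.
- Four days off: 39 − 8 = 31 doses (79.5%), below 32.
- Eight days off: 39 − 16 = 23 doses (59.0%). Withdrawal under Section 7.2.1 starts only beyond eight days.

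An interruption of four to eight days therefore leaves a subject on study, able to complete Cycle 1, and below 80%.

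**3. Compare the two rules, group by group.**

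| Subject in Cycle 1 | Section 7.2.2 | Section 10.2 |
|---|---|---|
| DLT-free, completes, under 80% intake | replaced | counted as DLT-free |
| DLT-free, stops for an unrelated adverse event | replaced | counted as DLT-free |
| DLT-free, at least 80% intake, stops for a reason that is not an adverse event | replaced | not counted |
| DLT, discontinues because of it | not replaced | counted as DLT |
| DLT, held, resumes, completes under 80% | replaced | counted as DLT |

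The rules conflict in rows 1 and 2. Row 5 is the gap in the exemption. Rows 3 and 4 agree.

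**4. Size of the dilution (rows 1 and 2).** The protocol gives no frequency, so these figures are illustrations.
- Two DLTs among six adequately dosed subjects: 2/6 = 33%. Adding two under-dosed DLT-free subjects: 2/8 = 25%.
- One DLT among four adequately dosed subjects: 1/4 = 25%. Adding two: 1/6 = 16.7%, on the other side of the 20% target.
- If a fraction u of the set is under-dosed and cannot show the DLT, the observed rate is the true rate × (1 − u). For a true 25%, it is 22.5%, 20.0% and 17.5% at u = 10%, 20% and 30%.

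**5. The held DLT subject (row 5).**
- Under Section 10.2 the DLT stays and a subject is added. With a DLT-free replacement, 2/6 becomes 2/7 = 29%, and 2/3 becomes 2/4, which still meets the Section 6 limit.
- If replacement is instead read as making the subject non-evaluable, the DLT is lost: 2/3 (limit met) would read as 1/3 (not met).

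**The case against.** **Completion may be defined elsewhere.** Completion of Cycle 1 is not given an intake condition here, Section 8.7 requires 80% compliance, and an SAP could add the floor. That is possible, but two sections of this protocol would still disagree, and replacement is decided during the trial from the protocol.

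**The under-dosed DLT-free group may be small.** Section 8.4.4 lets the investigator class a related toxicity that warrants withholding drug as a DLT. What remains is mainly missed doses and interruptions for other reasons. This stands and limits the size.

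**The dose decision is not mechanical.** The sponsor and investigators decide on all available safety data, guided by a Bayesian logistic model over all dose levels rather than by raw proportions. This also stands. In the 2/6 to 2/8 example both rates exceed 20%, and 2/6 does not reach the limit of 4 out of 6.

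Three stronger readings are tempting but not supported:
- A reader might infer that replacing a held DLT subject removes that DLT from the count. Section 10.2 keeps any DLT subject who completes Cycle 1.
- A reader might infer that both problems push the observed rate down together. They need opposite readings. If Section 10.2 governs, no completer's DLT is lost; if Section 7.2.2 governs, the under-dosed DLT-free subjects leave and the rate rises.
- A reader might add subjects who stop for reasons unrelated to any adverse event. Section 10.2 already excludes them, in line with Section 7.2.2.

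A reader might also infer that a DLT subject off drug for more than eight days drops out of Section 10.2, since the withdrawal is filed under non-compliance. That subject can equally be read as having discontinued because of the DLT. The text does not settle it.

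**Conclusion.** The inconsistency is real and concerns the analysis set of the primary variable. Followed as written, Section 10.2 counts as DLT-free two groups that Section 7.2.2 replaces as not evaluable for the MTD, and this dilutes the Cycle 1 DLT rate. The protocol's own dose counts show that the under-dosed group can arise. The size cannot be stated, because no frequency of under-dosing is given; the illustrated rates rest on assumed counts and on the premise that an under-dosed subject is less able to show a DLT. A bias of the final MTD in a given direction is not demonstrated.

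The missing exemption for a DLT subject who does not discontinue is a separate and lesser defect. A DLT is lost there only if replacement is taken to mean non-evaluable, which the stated purpose of Section 7.2.2 invites but Section 10.2 contradicts for completers.

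**What to change.** Use one definition of MTD-evaluable in both sections.
- Section 10.2: *The MTD set is every subject with a DLT in Cycle 1, whatever the intake or reason for stopping, plus every DLT-free subject who completed Cycle 1 with at least 80% of planned doses (Section 8.7).*
- Section 7.2.2: *Subjects with a Cycle 1 DLT are not replaced, whether or not they discontinue; replacement applies to subjects outside the MTD set.*

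Apply this set to the interim model, the count-based limits in Section 6, and the final model and MTD table in Section 10.4.2. State how a stop for related toxicity not classed as a DLT is handled: Section 7.2.2 currently does not replace it, and it would fall outside the new set.

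The sponsor must also reconcile the eight-day withdrawal limit in Section 7.2.1 with the delay of up to 21 days in Section 8.4.3. This review takes no view on which should apply.

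The cost is two sentences, no new data, and possibly a slightly smaller MTD denominator. If escalation is already complete, the final MTD analysis still needs the corrected set.

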## 6.2 Justification of the design - amended

For study objectives please see Section 4.

The study will be conducted at multiple sites worldwide to ensure recruitment of a sufficient number of subjects with advanced solid organ malignancies. The sites must be specialized in tumor assessment according to RECIST 1.1 and must be well equipped to conduct the efficacy and safety evaluations required by the protocol.

Only subjects for whom in the opinion of the investigator, experimental therapy with BAY 1163877 may be beneficial are allowed to participate. Life expectancy in most of those subjects is expected to be about 3 months. Dosing with BAY 1163877 may continue without evidence of tumor reduction or stable disease as long as, in the judgment of the investigator, some benefit is being derived. The inclusion of a placebo control or blinding of the treatment is considered not applicable for the objectives of this dose-escalation study (identification of MTD / RP2D).

The open-label, non-randomized, dose-escalating design is the standard design to define the safety profile, MTD, PK, PD biomarker and tumor response profile in subjects with advanced malignancies.

[figure not shown]
Once DLTs are reported, the use of adaptive dose-selection decisions according to prespecified safety rules based on actual DLT observations is chosen because it permits a better determination of the MTD with reduced sample size, while limiting the number of subjects being treated with toxic doses.

The "all-comers" design in study Part 1 will allow for expedited accrual of subjects and evaluation of safety in subjects with varied solid tumor types (any solid tumors).

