#### 9.3.1 Tumor evaluation - response assessment (RECIST)

In *measurable* lesions (i.e., at the primary site, visceral or nodal [in lymph nodes  $\geq$  1,5 cm] lesions), the objective response will be assessed by CT / MRI scan at the EOT visit and documented according to the revised RECIST guideline, Version 1.1 (RECIST, v1.1), see Section 16.8. The assessment will be done by the investigators. No central evaluation is planned for this study.

CT / MRI scans will be performed at the following time points:

- Screening (within 28 days prior to the first dose of BAY 1163877)
- At the end of Cycle 2 and every third subsequent Cycle (beginning with Cycle 5)

Results for these evaluations will be recorded with as much specificity as possible so that pre- and post-treatment results will provide the best opportunity for evaluation of tumor response.

A zero should be recorded when a lesion has completely resolved. Otherwise, disappearance of a lesion cannot be differentiated from a missing value.

The occurrence and location of new lesions should be recorded in the eCRF and the subject's medical records.

In general, the subject's best response assignment will depend on the achievement of both measurement and confirmation criteria (see Section 16.8).

If radiographic changes are believed by the investigator to be secondary to drug induced inflammation and not tumor progression, the investigator may postpone a diagnosis of progressive disease (PD) until the next radiographic evaluation in the study.

All scans should be done with the identical modality (CT or MRI) and the identical technique (e.g., slice thickness, field of view) to those obtained at baseline. For a response to be scored as complete response (CR) or partial response (PR), the response must be confirmed by a repeat CT scan (with contrast) or MRI scan (with and without contrast) performed not earlier than 4 weeks after the response was first determined.

No. BAY 1163877 / 16443

17 Oct 2018 Version 8.0 Page: 85 of 395

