#### 10.4.7 Efficacy data

Efficacy data, such as best tumor response, will be summarized using descriptive statistics and will be graphically displayed if appropriate. The correlation between pharmacodynamic parameters and selected safety, efficacy, or PK parameters may be graphically displayed. Further statistical analyses may be conducted.

The efficacy analysis will include descriptive analyses on response rate, progression-free survival (PFS) and time to progression (TTP).

**Response** as defined by RECIST v.1.1: complete response (CR), partial response (PR), stable disease (SD), progressive disease (PD), see Section 16.8.

**Progression-free survival (PFS)** is defined as the time (days) from the date of the first dose of study drug to the date of the first observed radiological disease progression or death, whatever comes first. PFS for subjects without tumor progression at the time of analysis will be censored at their last date of tumor evaluation.

**Time to progression (TTP)** is defined as the time from start of study treatment until objective tumor progression; TTP does not include deaths.

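### Limiting the efficacy set to subjects with post-baseline data inflates the response rate and leaves unclear whether deaths before the first scan count in PFS

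*Protocol*

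**What the plan says.** Section 10.2 defines two different populations. For safety it takes everyone treated: "All subjects who received at least one dose of the study medication will be included in the safety evaluation". For efficacy it adds a condition that can only be met after treatment has started: subjects given at least one dose "and who have post-baseline efficacy data available will be included in the efficacy evaluations".

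Section 10.4.7 names response rate, PFS and TTP as descriptive efficacy analyses. PFS runs from the first dose to "first observed radiological disease progression or death, whatever comes first". On censoring, "PFS for subjects without tumor progression at the time of analysis will be censored at their last date of tumor evaluation". Deaths are not events for TTP.

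Section 9.3.1 schedules scans at screening, at the end of Cycle 2 and every third cycle from Cycle 5. It requires a complete or partial response to be confirmed by a repeat scan at least 4 weeks later. On prognosis, Section 6.2 says: "Life expectancy in most of those subjects is expected to be about 3 months".

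**The concern.** The efficacy set selects on something observed after treatment starts. A subject who dies, or stops for toxicity or clinical decline, before any tumor assessment contributes nothing to the numerator and is also taken out of the denominator. The response rate then describes subjects who stayed long enough to be scanned, not those who were treated.

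Tumor response is a secondary objective. Part 2 looks for preliminary responses in lung, bladder, and head and neck cancer, and Part 3 adds further efficacy data. These rates will be read at face value. A confidence interval computed on the reduced denominator gives no sign of the shift.

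PFS raises a related question. If the set requires a tumor assessment, it drops deaths that Section 10.4.7 defines as events.

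**Working it through.** **Inputs.** Cycles last 21 days (Section 6), so the first scheduled scan falls at 2 × 21 = day 42, and later scans come every 3 × 21 = 63 days. Section 10.7 sets expansion groups of about 20 subjects, and 30 to 50 for bladder cancer in Part 2. It performs no formal sample size estimation, and no target response rate is stated, so there is no planned figure to reproduce. The share d of treated subjects without a post-baseline assessment is not in the protocol; 5% to 30% is assumed.

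**1. Response rate.** A response needs post-baseline scans, so every responder is in the restricted set and everyone excluded for lack of an assessment is a non-responder. With x responders among N treated:

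- all treated: x/N
- restricted set: x/[N(1-d)]
- ratio: 1/(1-d), which is 1.05 at d = 5%, 1.11 at 10%, 1.25 at 20% and 1.43 at 30%

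For x = 10 and N = 50 (20.0%), in whole subjects:

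- 2 excluded (4%, the whole number just below 5%): 10/48 = 20.8%
- 5 excluded (10%): 10/45 = 22.2%
- 10 excluded (20%): 10/40 = 25.0%
- 15 excluded (30%): 10/35 = 28.6%

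For 4/20 (20.0%) with 4 excluded: 4/16 = 25.0%.

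**2. How large d might be from deaths alone.** With exponential survival of median m days, the share dead by day 42 is 1 - 2^(-42/m). The all-treated rate is taken as 20%.

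- m = 91: 27.4%; the rate becomes 20/0.726 = 27.5%
- m = 182: 14.8%; 20/0.852 = 23.5%
- m = 365: 7.7%; 20/0.923 = 21.7%

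**3. PFS, if the set requires a scan.** Kaplan-Meier estimates from 40,000 simulated subjects, with scans at day 42 and every 63 days after. Assumptions: exponential progression with median 84 days, exponential survival, and 0% or 10% stopping before the first scan. Subjects who stop without a scan are censored at day 1.

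| Median survival | Early stopping | No scan | Day-84 PFS, all treated vs restricted | Median PFS, all treated vs restricted |
|---|---|---|---|---|
| 91 d | 0% | 27.2% | 37.1% vs 51.0% | 46 vs 87 d |
| 182 d | 0% | 14.7% | 51.1% vs 59.9% | 90 vs 105 d |
| 182 d | 10% | 23.5% | 51.2% vs 60.8% | 92 vs 105 d |
| 365 d | 10% | 16.9% | 60.2% vs 65.4% | 105 vs 105 d |

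The shift at day 84 is about 5 to 14 percentage points. It comes from the deaths. Removing only those who stopped alive without a scan leaves day-84 PFS at 51.2% (median survival 182 d), and moves it from 60.2% to 60.1% (365 d).

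**4. TTP.** In the same scenarios median TTP is 105 days in both sets. The day-84 estimates, 70% to 71%, differ by at most 0.2 points, and downward if anything.

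**The case against.** **The wording is efficacy data, not scan.** Section 10.4.7 makes death a PFS event, so a death date could itself count as post-baseline efficacy data. On that reading the PFS bias disappears. Early deaths also stay in the set for response, and d shrinks to those who stopped alive without an assessment. This stands as a possible reading, but the protocol does not say which applies. On either reading, whoever is excluded for want of an assessment is a non-responder.

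**There may be a scan at end of treatment.** The opening of Section 9.3.1 mentions one, which would keep some early stoppers in the set. It is missing from that section's own list of scan times and from the end-of-treatment visit in Section 9.1.2.3.4. The passages must be reconciled. Until then it can only be said that d may be smaller.

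**27% is pessimistic.** Section 7.1.1 requires a life expectancy of at least 3 months and ECOG 0 to 2, which sits badly with a constant hazard that kills 27% by day 42. This is right, and 27% should be read as an upper-end case.

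**Efficacy is descriptive.** There is no efficacy test or decision rule, Section 10.1 has all data listed, and at 10/50 the exact 95% interval is 10.0% to 33.7%, so the shift is small beside sampling error. That lowers the severity. It does not remove a bias that goes one way only.

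**Section 16.8.** The best-response rules there were not available to check. They could settle how unassessed subjects are classified, but they would not change the set defined in Section 10.2.

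A reader might go further and infer that TTP is inflated, or that early stoppers bias PFS through this set. Neither follows. Deaths are not TTP events, and stoppers without a scan would be censored at the start, so removing them changes essentially nothing. Informative censoring may still matter there, but the analysis set does not cause it. Nor does Section 10.4.7 plan a formal comparison between tumor types that this would invalidate.

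**Conclusion.** The point holds for the response rate. The rule in Section 10.2 multiplies the all-treated rate by 1/(1-d), always upward. The direction needs no assumption beyond some treated subjects lacking an assessment; the size rests on d, which the protocol does not give. Across the assumed range a 20% rate in 50 subjects is reported as 20.8% to 28.6%.

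For PFS the point is conditional. If efficacy data means a tumor assessment, deaths before the first scan are lost and Sections 10.2 and 10.4.7 conflict, with day-84 PFS overstated by about 5 to 14 points in the scenarios run. If a death counts as efficacy data, there is no such bias. The protocol should say which is meant. TTP, and PFS for subjects who stop without a scan, are not biased by this set.

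Severity is moderate: the endpoint is secondary, the analyses are descriptive and no decision rule depends on them.

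**What to change.** In Section 10.2:

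- define the efficacy set as every subject given at least one dose of BAY 1163877, the same population as for safety;
- count a subject without a post-baseline tumor assessment as a non-responder in the response rate, shown as not evaluable;
- state that a death before the first scan is a PFS event on its date, in line with Section 10.4.7;
- keep the response-evaluable set as a supplementary table, labelled as such, with the number excluded.

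The change is one of wording and needs no new data. Its cost is that reported response rates become somewhat lower.
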